10.2 Premature termination of the clinical study

- Unjustifiable risk in risk-benefit analysis (decision taken by principal Investigator)
- New scientific evidence provided during the study that could affect the patient's safety (benefit-risk analysis no longer positive)

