5.3 Endpoints Committee

The Endpoints Committee will be composed of cardiologists and ED physicians. This Committee is responsible for assessing the primary and secondary efficacy endpoints.

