8.5 Registration

Patients, who meet all inclusion criteria, who have given their written informed consent and have been randomized will be reported to the trial centre via Fax.:

- BIC-Trials
- [name]

The following data are to be included in this registration FAX (attachment 6)

- Study site, Investigator
- Pseudonym of patient
- Gender
- Randomization group

The trial centre will regularly (1x/week) update the members of the steering committee on the numbers and basic characteristics (s. above) of patients enrolled.

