8.9 Additional 3 hour blood test

Patients can, on an optional basis, agree to an additional, study-related blood draw at 3 hours after their initial admission. This blood sample will be used to further evaluate the kinetics of Copeptin. Additionally, Troponin will be measured to compare the two markers in these samples.

Patients who agree to the blood draw have to give their separate written consent in a special box of the informed consent form (s. attachment).

9 Risk-benefit-assessment

Copeptin negative patients might experience major adverse cardiac events after discharge, which could have been prevented in case of hospital admission, due to unrecognized acute coronary syndrome.

Precaution:

Patients for this trial are very carefully selected. Patients with concomitant diseases or conditions which require a hospitalisation as well as patients with instable angina despite maximal therapy are excluded from participation. Thus, only stable, symptom-free patients will be discharged. We cannot exclude that of these patients, some will be at risk for ACS-related complications. As a precaution, patients will only be discharged after an appointment with one of our co-operating resident cardiologists has been made via the praxis-connect system as explained in section 7.1. Thus, the onward specialist care of these patients is guaranteed. The co-operating cardiologists will be well informed and trained in all trial-matters. All patients will be re-admitted to the Emergency Department upon any suspicion of risk for complications.

Copeptin positive patients might be regarded as high-risk patients and receive more intensive treatment.

Precaution:

Management of all patients will be closely monitored by the principal investigator of each site to assure suitable care and therapy.

Potential advantages for patients in the experimental arm:

Copeptin negative patients bypass further ACS evaluation and are prevented from hospitalization. Patients might be spared an unnecessary hospital admission and antithrombotic and anticoagulant treatment with their related hazards and side-effects. Patients will profit from the personal care by the resident co-operating cardiologist.

All patients will profit from the close and intense monitoring and follow-up by an experienced clinical research team.

Potential advantages for the general public:

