11.1 Definition

Major adverse cardiac event (MACE) is defined as

- All- cause death or survived sudden cardiac arrest
- myocardial infarction
- Re-hospitalisation for acute coronary syndrome
- Acute unplanned PCI
- Coronary artery bypass grafting (CABG)
- Documented life-threatening arrhythmias (VF, VT, AV-block III)

Major bleeding is defined as

- Non-CABG intracranial, intraocular, or retroperitoneal bleeding
- Access-site hemorrhage requiring intervention or resulting in a ≥ 5 cm diameter hematoma
- Reduction in hemoglobin concentration of ≥ 4 g/dL without or ≥ 3 g/dL with an overt bleeding source
- Reoperation for bleeding
- Blood product transfusion

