11.2 Documentation of MACE and major bleeding events

All MACE and major bleeding events will be documented, no matter if the Investigator suspects a causal connection to the investigational process or not.

The event will be recorded in the CRF.

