11.3 Reporting of MACE and major bleeding events

The Investigator will report any MACE or major bleeding event within 1 week after his/her knowledge of the event to the Sponsor. This announcement will be done via telephone or fax to:

BIC-Trials

[contact]

[contact]

The Investigator will write a written record describing the event, its cause, treatment and outcome.

Exceptional rules:

In this clinical trial the following Serious Adverse Events are excluded from the notification requirement:

- Severe or unexpected events which occur after enrolment, but before the experimental process was initiated

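### Section 10.2 leaves a stop for harm to the principal investigator's judgement without criteria, and no visible passage plans a comparison of MACE by arm during recruitment

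*Protocol*

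**What the plan says.** Section 10.2 lists two grounds for ending the study early. The first is "Unjustifiable risk in risk-benefit analysis (decision taken by principal Investigator"; the second begins "New scientific evidence provided during the study that could affect" and concerns patient safety. Neither states what is compared, when, from which data, or what result would lead to a stop.

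Section 9 puts the hazard plainly: "Copeptin negative patients might experience major adverse cardiac events after discharge, which could have been prevented in case of hospital admission".

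The other visible arrangements are these:

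- **Event records.** Section 11.2 covers all MACE and major bleeds, whatever the suspected cause: "The event will be recorded in the CRF". Section 13.1 has the eCRF data go directly to the study centre's database.
- **Event reports.** Section 11.3 has each MACE or major bleed reported to the sponsor within 1 week, with a written account.
- **Steering committee.** Under section 8.5 the trial centre receives each patient's randomisation group, and every week it will "update the members of the steering committee on the numbers and basic characteristics (s. above) of patients enrolled". Outcomes are not part of that update.
- **Endpoints Committee.** Section 5.3: "This Committee is responsible for assessing the primary and secondary efficacy endpoints". It is given no role in stopping.
- **Protection of single patients and of conduct.** These are the exclusions (6.2), the cardiologist visit within 3 days (7.1), site principal investigators watching patient management (9), and quality assurance and monitoring (12.1).

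**The concern.** The experimental process withholds further ACS evaluation from Copeptin-negative patients and sends them home. The primary endpoint, MACE within 30 days, measures the harm that section 9 says this could cause. Some MACE is expected in both arms, so a single report, however well written up, does not show whether the Copeptin arm has too many. That takes a comparison of the arms. The data for it are held centrally, but no visible passage asks anyone to make it before recruitment ends at the planned 892 patients.

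Section 10.2 is where the protocol fixes how the trial may be stopped. It does so by a judgement whose evidence, timing and threshold are left open. If early discharge caused a large excess of MACE, acting on it would depend on someone choosing to look.

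**Working it through.** **1. Does any visible safeguard amount to a planned comparison by arm?**

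| Place | What it does | Compares MACE by arm? |
|---|---|---|
| 5.3 | assesses endpoints | no |
| 6.2, 7.1 | protects single patients | no |
| 8.5 | weekly enrolment figures | no outcomes |
| 9 | site-level oversight of management | no |
| 11.2, 11.3 | records and reports single events | no tabulation |
| 12.1 | quality assurance and monitoring | no |
| 10.2 | risk-benefit judgement | possible, not specified |

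**2. Inputs for judging a possible review**

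- Sample size 446 per arm, 892 in total, 1:1 (synopsis). The power calculation is in an appendix that is not shown, so 446 cannot be reproduced. The point does not depend on it.
- Control MACE rate: assumed 5% to 6.4%. Section 14.2.2 cites 6.4%, but at 6 weeks and in serially Troponin-negative patients, so it is only a guide. The 5% is an assumption.
- Copeptin-negative share: not stated; assumed 60% to 80%.
- Looks at about 25% and 50%: 112 and 223 per arm with 30-day data.
- Prompt: one-sided Fisher exact p<0.05 for more MACE in the Copeptin arm.

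**3. What the limit means in counts.** At 223 per arm, 11 control events need at least 21 in the Copeptin arm, and 14 need at least 25.

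**4. Dilution.** Only Copeptin-negative patients are managed differently. If their share is q, their baseline risk equals that of the positives, and MACE doubles among them, the whole-arm ratio is 1 + q:

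- q = 0.6 gives 1.6; q = 0.8 gives 1.8.
- If the negatives have half the baseline risk of the positives, the ratio is 1 + 0.5q / (0.5q + 1 − q). This gives 1 + 0.3/0.7 = 1.43 and 1 + 0.4/0.6 = 1.67.
- Conversely, a whole-arm doubling at equal baseline risk needs a ratio of 1 + 1/q among those discharged, that is 2.67 (q = 0.6) or 2.25 (q = 0.8).

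**5. Chance that a review is prompted by the second look** (simulation of the rule in step 2; control rate 5% and 6.4%)

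| Scenario | 5% | 6.4% |
|---|---|---|
| equal rates | 4.6% | 5.0% |
| whole arm 1.5-fold | 27% | 33% |
| whole arm 1.6-fold | 33% | 41% |
| whole arm 1.8-fold | 48% | 58% |
| whole arm 2-fold | 62% | 72% |
| re-hospitalisation alone adds 1 point | 11% | 11% |
| re-hospitalisation alone adds 2 points | 21% | 19% |

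A doubling among discharged patients corresponds to the 1.6- to 1.8-fold rows, so about 33% to 58%. At half the baseline risk (1.4- to 1.7-fold overall) it is about 21% to 49%. With the 7.8% that section 14.2.2 also cites as the control rate, equal rates give about 5%, 1.6- to 1.8-fold gives 48% to 67%, and a doubling 81%.

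If only the severe components are tested (assumed to be half of MACE, 2.5% to 3.2%), a doubling is flagged by the second look in 34% to 43%.

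**6. What remains to be protected at the second look.** With even recruitment over 12 months, about 73 more patients enrol during the 30 days (892 × 30/365). Enrolment at the looks is then 224 + 73 = 297 (33%) and 446 + 73 = 519 (58%). After the second look 892 − 519 = 373 remain, about 186.5 of them in the Copeptin arm. Of these, 186.5 × 0.6 = 112 to 186.5 × 0.8 = 149 would be discharged early. If MACE doubles among them, the excess still to come is 112 × 0.05 = 5.6 to 149 × 0.064 = 9.5 events. A look at 75% would fall at (670 + 73)/892 = 83% of enrolment and would protect few further patients.

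**The case against.** The strongest objection is that this is an absence and not an error. A stop on risk-benefit grounds is a real rule, and its details are often kept in a monitoring charter or the SAP, neither of which is shown. The steering committee is mentioned but never set up in the visible text, which suggests that some oversight text lies elsewhere. This stands as a limit on the finding: if such a document sets the review, a reference is all that is needed. It does not remove the point, because section 10.2 itself states how the trial may be stopped and does so without criteria.

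Three stronger readings are tempting, and the documents do not support them.

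- **That harm would go unreviewed.** Each MACE reaches the sponsor within a week with a written account, an Endpoints Committee assesses endpoints, and a risk-benefit judgement presupposes looking at risks. What is lacking is a planned comparison by arm.
- **That only a pooled rate would be visible, which cannot separate harm from a higher-risk population.** The trial is open and its centre holds both arm and events. Nothing confines anyone to pooled data.
- **That the exemption in section 11.3 makes event reports differ by arm.** It covers "Severe or unexpected events which occur after enrolment, but before the experimental process was initiated". The experimental process is not defined there, and section 7 describes the standard process under the investigational one. The interval may also be short, since Copeptin is run on the routine sample with 14 minutes' incubation. Differential reporting is conjecture.

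It is also fair to say that a whole-arm doubling flatters any such review, because Copeptin-positive patients dilute the effect. The figures above therefore start from a doubling among discharged patients.

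**Conclusion.** The point holds in limited form. Section 10.2 rests a stop on the trial's own events on a judgement without criteria, and no visible passage requires MACE to be compared by arm during recruitment, although section 9 lists avoidable MACE after early discharge as its first hazard. An ad hoc comparison is possible but not required.

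The gain from a planned review is real but moderate. By the second look it is prompted in about 5% of trials with equal rates, about 33% to 58% if MACE doubles among discharged patients, and 62% to 72% if the whole-arm rate doubles. These figures rest on an assumed control rate of 5% to 6.4%, a Copeptin-negative share of 60% to 80%, equal baseline risk in Copeptin-negative and Copeptin-positive patients, and even recruitment. The review is a guard against large harm and cannot show safety. No stated figure in the protocol is shown to be wrong.

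**What to change.** Add one paragraph to section 10.2, or refer there to the charter or SAP if one already sets this:

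- **When.** At about 25% and 50% of patients with 30-day data.
- **What.** The trial centre tabulates MACE by arm from the eCRF, counted from randomisation. Death, arrest, MI and life-threatening arrhythmia are shown apart from revascularisation and from the component "Re-hospitalisation for acute coronary syndrome". Post-discharge events in discharged Copeptin-negative patients are listed.
- **Who.** The table goes in confidence to steering committee members who neither enrol patients nor adjudicate events.
- **Limit.** A one-sided Fisher p<0.05 for excess MACE in the Copeptin arm prompts a documented review and a recommendation on pausing or stopping. It is not an automatic stop. The components are read first, since an excess confined to re-hospitalisation need not be harm.
- **Limits of inference.** State that not crossing the limit does not show safety and that the review cannot support an early claim of safety.

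The cost is a paragraph and two short tables from data already held, with no extra patients. The visible text does not give the steering committee's membership, so one or two suitable people may have to be named. The downsides are an unneeded meeting in about 5% of trials with equal rates (about 11% to 21% if early discharge only adds 1 to 2 points of re-hospitalisation), the use of unadjudicated events, and by-arm results seen by a few people in an open trial. A harm-only review does not raise the chance of a false claim of safety.

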10.3 Follow-up and continuing treatment after regular / premature termination

All patients who have not been excluded from participation will be contacted via telephone for a 30 day follow-up to assess MACE and bleeding events.

All patients will be contacted via telephone after 90 days to assess MACE and bleeding events. All efforts should be made to contact all patients for the 90 day follow-up telephone visit, if the consent to do so is granted.

11 Assessment of MACE and bleeding events

11.1 Definition

Major adverse cardiac event (MACE) is defined as

- All- cause death or survived sudden cardiac arrest
- myocardial infarction
- Re-hospitalisation for acute coronary syndrome
- Acute unplanned PCI
- Coronary artery bypass grafting (CABG)
- Documented life-threatening arrhythmias (VF, VT, AV-block III)

Major bleeding is defined as

- Non-CABG intracranial, intraocular, or retroperitoneal bleeding
- Access-site hemorrhage requiring intervention or resulting in a ≥ 5 cm diameter hematoma
- Reduction in hemoglobin concentration of ≥ 4 g/dL without or ≥ 3 g/dL with an overt bleeding source
- Reoperation for bleeding
- Blood product transfusion

11.2 Documentation of MACE and major bleeding events

All MACE and major bleeding events will be documented, no matter if the Investigator suspects a causal connection to the investigational process or not.

The event will be recorded in the CRF.

11.3 Reporting of MACE and major bleeding events

The Investigator will report any MACE or major bleeding event within 1 week after his/her knowledge of the event to the Sponsor. This announcement will be done via telephone or fax to:

BIC-Trials

[contact]

[contact]

The Investigator will write a written record describing the event, its cause, treatment and outcome.

Exceptional rules:

In this clinical trial the following Serious Adverse Events are excluded from the notification requirement:

- Severe or unexpected events which occur after enrolment, but before the experimental process was initiated

11.4 Investigator Site File (ISF)

All essential documents will be kept in the Investigator Site File which will be stored at the study site in accordance with ICH GCP.

12 Quality management

12.1 Control of trial progress and data quality

1. Quality Assurance (QA) is maintained to meet practice standards required by the ethics committee.
2. Identification of Deficiencies- QA standards are set to insure that patient safety and protocol mandated procedures are being met, and that any variances are identified, reported to the responsible committees and investigators for remedial action.

3. Corrective Action Plan- A plan to correct for deficiencies will be initiated when such deficiencies are deemed of a severity requiring remediation. Such an action plan will be governed by the guidelines of the QA practice standards maintained as stated in section 1.

12.1.1 Monitoring

The sponsor will contact the sites prior to the start of the study to review with the site staff the protocol, study requirements, and their responsibilities to satisfy regulatory and ethical, requirements. When reviewing data collection procedures, the discussion will include identification, agreement and documentation of data items for which the CRF will serve as the source document.

The sponsor will monitor the study to ensure that the:

- Data are authentic, accurate, and complete.
- Safety and rights of subjects are being protected.
- Study is conducted in accordance with the currently approved protocol and any other study agreements, GCP, and all applicable regulatory requirements.

The investigator and the head of the medical institution (where applicable) agrees to allow the monitor direct access to all relevant documents.

12.1.2 Audits / inspections

At its discretion, the sponsor may conduct a quality assurance audit of this trial. If such an audit occurs, the investigator agrees to allow the auditor direct access to all relevant documents and to allocate his/her time and the time of his/her staff to the auditor to discuss findings and any relevant issues. In addition, regulatory agencies may conduct a regulatory inspection of this trial. If such an inspection occurs, the investigator agrees to allow the inspector direct access to all relevant documents and to allocate his/her time and the time of his/her staff to the inspector to discuss findings and any relevant issues.

13 Data entry und data management

All patient related data will be recorded under a pseudonym. Every patient will receive a patient number / pseudonym which will be unique for this individual patient. The Investigator will compile a confidential list, which relates these patient numbers to the patient's full name. This list will only be accessible to the study team and the monitor. Original patient files may be viewed by monitors, auditors and inspectors.

13.1 Data collection / documentation form

All data will be recorded in an electronic Case Report Form.

All data will be recorded online and will be transmitted directly to the database of the study centre. Data will be transferred between the workstation computer at the study site and the study server via a secure connection (secure socket layer /SSL) so that the data cannot be manipulated.

13.2 Data processing

The Sponsor will file all data electronically. To verify accuracy of the data, range, validity and consistency checks will be performed. Implausible or missing data can be corrected or added after consulting the Investigator. Documentation for these corrections will be stored with the CRFs.

All validated data will be stored in the eCRF. After termination of the study and after completion of all entries, the database will be closed (frozen) for further entries. This process will be documented.

13.3 Generation of pseudonym

All patient data will be saved under a pseudonym. The study software will automatically generate a pseudonym for every new patient/the pseudonym for new patients can be typed into the study software. A document for clear patient allocation will be printed and must be kept in a safe place.

14 Statistical Analysis

14.1 Sample size estimation

See appendix 2

14.2 Statistical analysis

14.2.1 Definition of population for analysis

First a check of the success of randomisation will be conducted: Bivariate comparisons of basic demographics and baseline risk-markers between experimental group and control group .

Exact Fisher tests will be conducted for comparison of proportions of the main outcome in case of a successful randomisation. But logistic regression analysis will also be employed to adjust for potential confounding.

If more than 10% of patients are lost during follow-up, additional intention to treat analyses will be conducted.

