Objectives	To quantify the benefit of integrating the new biomarker Copeptin into the process of managing patients with suspected non ST-elevation acute coronary syndrome (N-STEACS) with a negative baseline Troponin test result in the Emergency Department. Hypothesis : Patients with suspected ACS with a negative baseline Troponin who test negative for Copeptin at admission are at low risk of ACS and can safely be discharged into ambulant care. Secondary hypotheses: Patients with suspected ACS with a negative baseline Troponin who test positive for Copeptin at admission are at risk for ACS and should be evaluated as by standard of care. The Integration of Copeptin into the CPU process will shorten the patient's length of Emergency Department/ CPU and hospital stay and will improve patient satisfaction.
Study Design	Multicentre, open, randomized, controlled clinical trial (RCT) Interventional diagnostic biomarker trial 1:1 Randomization in two study arms with differing process management: a) interventional/experimental arm (Integration of Copeptin) b) control/ standard arm (Copeptin not available to treating staff)
Number of Sites	3 sites in Germany, 1 site in Switzerland and 1 site in Austria
Experimental Diagnostic Process	Experimental Arm: Patients with the above described characteristics who test negative for Copeptin at admission will be considered low-risk and will be discharged into ambulant care without further interventions. Patients with the above described characteristics who test positive for Copeptin at admission will be evaluated as by standard of care according to current guidelines..
Standard Diagnostic	Control Arm:

Process	Copeptin result will not be revealed to the treating physicians. Patients will be evaluated as by standard of care according to current guidelines.
Gold Standard	DGK / ESC / AHA Guidelines for the management of patients with suspected Non-ST-elevation ACS (NSTEMACS)
Time Schedule	Date of study / recruitment start: February 2011 Date of termination of recruitment: February 2012 Date of study termination: Autumn 2012
Total Number of Patients	n=446 per treatment group (total number of patients 892)
Study Population	Men and women of full age with suspected Non-ST-elevation acute coronary syndrome (NSTEMACS) and negative baseline Troponin.

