5 Study objectives

This is a multicentre biomarker randomized controlled trial to quantify the benefit of integrating the new biomarker Copeptin into the process of managing patients with suspected non ST-elevation acute coronary syndrome (N-STEACS) with a negative baseline Troponin I test result in the Emergency Department and Chest Pain Unit.

Hypothesis:

Patients with suspected ACS with a negative baseline Troponin who test negative for Copeptin at admission are at low risk of ACS and can safely be discharged into ambulant

care. These patients will not experience a higher rate of MACE within 30 days after their admission than patients who are managed by standard practise of care.

Secondary hypotheses:

Patients with suspected ACS with a negative baseline Troponin T who test positive for Copeptin at admission are at risk for ACS and should be evaluated as by standard of care. The Integration of Copeptin into the CPU process will shorten the patient's length of Emergency Department/ CPU and hospital stay and will improve patient satisfaction

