14.2.2 Analysis of endpoint

Safety of discharging patients with negative Troponin and negative Copeptin at baseline We chose a primary safety endpoint to prove that discharge of these patients does not increase their mortality or their risk for cardiac events like survived sudden cardiac arrest, myocardial infarction, re-hospitalisation for acute coronary syndrome, acute unplanned PCI, coronary artery bypass grafting (CABG) and documented life-threatening arrhythmias (VF, VT, AV-block III). [name] et al. saw a 6 week MACE rate of 6.4% in 266 patients with a serial negative Troponin result, who were evaluated for an acute coronary syndrome and a 7.8% MACE rate in all patients who were sent home after judgment of the attending physician.

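### The aim is to prove that copeptin-guided discharge does not raise 30-day MACE, but the test fixed for the main outcome is a Fisher test of equal rates, which cannot show that

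*Protocol*

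**What the plan says.** Section 5 (Study objectives) gives the hypothesis for copeptin-negative patients discharged early: "These patients will not experience a higher rate of MACE within 30 days after their admission than patients who are managed by standard practise". Section 14.2.2 gives the purpose of the primary endpoint: "We chose a primary safety endpoint to prove that discharge of these patients does not increase their mortality or their risk for cardiac events". Both describe a claim of no excess risk.

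Section 14.2.1 names the analysis, provided randomisation has worked: "Exact Fisher tests will be conducted for comparison of proportions of the main outcome". It continues: "But logistic regression analysis will also be employed to adjust for potential confounding". Section 14.2.3 adds that the main findings will be validated by multivariable logistic regression even if randomisation has worked. None of these sections states a margin, a one-sided bound, an alpha level or a rule based on a confidence limit.

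The synopsis gives 446 patients per arm, 892 in total, randomised 1:1. Section 14.1 refers to appendix 2 for the basis of that number, and the appendix is not reproduced in the text at hand.

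**The concern.** A Fisher test asks whether the data are incompatible with equal rates. Rejection shows a difference. Non-rejection can mean equal rates, or too little information to tell. It therefore cannot establish that MACE is not higher, which is the claim the protocol sets out to prove. Under such a test, anything that lowers power makes a non-significant result more likely.

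The logistic regression would give an interval for an odds ratio, but no limit is stated against which to judge it, so it does not fill the gap.

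The safety conclusion is the purpose of the trial: the experimental process discharges patients without further ACS evaluation (section 7.1), and section 9 accepts that some preventable events may follow. If the conclusion does not follow from the prespecified analysis, the main result has no firm basis even when the data are good.

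**Working it through.** **Inputs.** 446 per arm and 1:1 allocation come from the synopsis. For event rates, section 14.2.2 cites a study that "saw a 6 week MACE rate of 6.4% in 266 patients with a serial negative Troponin result" and reports 7.8% in patients sent home. I take 7% as the control rate (assumed, between the two) and two-sided alpha 0.05 (assumed; neither sidedness nor alpha is stated).

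**The plan's own figure.** 446 cannot be reproduced, because the text shown gives no alpha, power or margin.
- As a difference test of 6.4% versus 7.8% it does not fit: one- or two-sided 0.05, 80% or 90% power, with or without continuity correction, the requirement is 4,161 to 7,213 per arm.
- As a non-inferiority size, n = 2p(1−p)(z_α + z_β)²/margin², several sets come close. With p = 7%, margin 5 points, one-sided 5% and 90% power: 2 × 0.07 × 0.93 × (1.645 + 1.282)²/0.05² ≈ 446. With p = 10%, 5 points, one-sided 5% and 80% power: 446. With p = 7.8%, 5 points, one-sided 2.5% and 80% power: 452.

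The fit is not unique, so it does not show which inputs were used.

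**How often Fisher's test misses a true excess.** For each pair of true rates, the binomial probabilities of all outcome pairs with two-sided Fisher p > 0.05 are summed, at 446 per arm:

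| True excess | Control 6.4% | Control 7% | Control 7.8% |
|---|---|---|---|
| 2 points | 83% | 84% | 85% |
| 3 points | 67% | 68% | 70% |
| 4 points | 47% | 49% | 52% |
| 5 points | 29% | 31% | 35% |

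**A single result.** Take 31/446 (7.0%) in the control arm and 48/446 (10.8%) in the experimental arm.
- Fisher two-sided p = 0.059: not significant. One more event (31 versus 49) gives p = 0.046.
- Difference = 0.1076 − 0.0695 = 0.0381.
- Standard error = √(0.0695 × 0.9305/446 + 0.1076 × 0.8924/446) = 0.0190.
- Wald 95% interval: 0.0381 ± 1.96 × 0.0190, about +0.1 to +7.5 points.

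The two methods disagree slightly at the border because Fisher's test is conservative. A non-significant Fisher result is thus compatible with an excess of about 7 points. With equal arms the one-sided p is half the two-sided one, 0.059/2 ≈ 0.029, so a one-sided test at 0.05 would flag this result and one at 0.025 would not. Sidedness moves the border; it does not turn non-significance into evidence of safety.

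**What 446 per arm would give under a margin rule.** With equal true rates p, power = Φ(margin/√(2p(1−p)/446) − 1.96) at one-sided 0.025.
- p = 6.4%: standard error √(2 × 0.064 × 0.936/446) = 0.0164. For 5 points, 0.05/0.0164 = 3.05, power 86%. For 3 points, 1.83, power 45%.
- p = 7.8%: standard error 0.0180. For 5 points, 2.78, power 80%. For 3 points, 1.67, power 39%.

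These margins are illustrations; none appears in the text shown.

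**The case against.** The strongest reply is that the decision rule may sit in appendix 2 or in a statistical analysis plan, neither of which is shown. That stands as far as it goes: it cannot be said that the trial has no margin, and the absence of one from this text is not the point. The point is the test that section 14.2.1 does fix. If appendix 2 uses a margin, that section departs from it and should be aligned.

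A reader might infer several stronger things that the protocol does not support:

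- *That the plan will treat a non-significant p-value as proof of safety.* No success rule is written. This is only the evident route from the stated test to the stated aim.
- *That an important rise in MACE would most likely be missed.* This holds for rises below about 4 points. At 4 points it is roughly even, and a 5-point rise is detected 65% to 71% of the time. The text shown does not say which rise matters clinically.
- *That 446 was derived from a non-inferiority calculation.* The number fits one, but several input sets fit about equally well.
- *That changing the analysis leaves the trial adequately sized.* At one-sided 0.025 this is so only if the margin is near 5 points.

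The logistic regression also deserves mention, since it would yield an interval estimate. Without a stated limit, it does not supply the missing rule.

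**Conclusion.** The mismatch is real and lies in the protocol's own wording: a claim of no increase is paired with a test of equality. This is a wrongly chosen method for the stated aim, and it should be corrected before the results are analysed. That conclusion follows from the logic of the test and needs no assumed figure. The size of the problem rests on two-sided 0.05, full enrolment of 446 per arm with no loss, and a control rate near the quoted 6.4% to 7.8%. Under these, the test leaves excesses of 2 to 3 points undetected about two-thirds of the time or more, and 4 points about half the time. How serious this is depends on the excess the trial regards as relevant, which only appendix 2 may show.

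**What to change.** In section 14.2:

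- Make the primary analysis a confidence interval for the 30-day MACE risk difference, experimental minus control. Conclude that there is no relevant excess only if the upper limit lies below a prespecified, justified margin at a stated one-sided alpha.
- Take the margin and alpha from appendix 2 if it contains them. Otherwise set and justify them before any outcome comparison by arm has been seen, and state the power that 446 per arm then gives.
- Keep Fisher's test as descriptive and the logistic regression as supportive.
- State that a non-significant difference is not evidence of safety, and word the hypothesis in section 5 to match.

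The cost is a rewording, a stricter success criterion and possibly a less favourable stated power. No new data are needed and no change in enrolment is proposed; whether 446 per arm suffices depends on the margin.
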